5.2.3. Analyses for Categorical Data

The frequency and percentage for each category will be presented.

5.2.4. Analyses for Time to Event Data

For all time to event analyses, an origin and an accrual period will be defined (see table below), depending on the analysis populations. For a subject who experiences the event, the time to event will be the study day (relative to the origin being used for the analysis) corresponding to the actual date of the event or the earliest visit date at which the subject has already experienced the event. For all subjects who have not experienced the event and reached the end of the accrual period, their time to event will be right censored at the end of the accrual period. For subjects who permanently discontinue before the end of the accrual period without experiencing the event, their time to event will be considered missing data (see [Section 5.3.3](#) for handling of missing data in analysis).

	Origin	End of the Accrual Period
FAS-OL	Study Baseline	Last dose of open-label, run-in treatment
FAS-RA	First dose of randomized treatment	Last dose of randomized treatment
FAS-RE	Rescue Baseline	Last dose of rescue treatment

Time-to-event endpoints will be summarized using the Kaplan-Meier method and estimated survival curves will be displayed graphically. Graphs will describe the number of patients at risk over time. The median, quartiles and probabilities of not having an event at particular points in time will be estimated by the Kaplan-Meier method and their 95% CIs will also be provided when the data allows for their calculation. For some analyses, treatment differences between the probabilities of not having the event may be reported. Wald-type CIs for such differences will be reported using standard errors for the probabilities based on Greenwood's formula.

The log-rank test (stratified using age group [adults and adolescents] and disease severity [moderate and severe] at Study Baseline) p-value will be used for comparing time to event data between treatment groups.

For some analyses, a Cox regression model will be fit with treatment, age group and disease severity at Study Baseline as covariates. The estimated hazard ratio for the three pairwise treatment comparisons and its 95% CI will be reported from this model. For subgroup analyses, we will only have fixed effect of treatment in the model.

5.3. Methods to Manage Missing Data

In general, for analyses using descriptive statistics, missing values will not be imputed. In addition, for safety endpoints, missing values will not be imputed. Other methods for handling missing values are discussed below.

5.3.1. Binary Endpoints

In the context of analyses based on the FAS-RA analysis set, some subjects may enter the rescue phase of the study. This intercurrent event (receiving rescue treatment after randomization) may be considered a dropout from randomized treatment with regard to the effect of the treatment difference for various efficacy measurements as compared among the three different randomized treatments during the double-blind period. This implies that outcome values after this intercurrent event will be considered missing data.

One way to handle the missing observations is to define responses for all subjects who dropout for any reason, including a protocol-defined flare, to be "non-responsive" at all subsequent visits from first rescue dosing date (for subjects who get rescue treatment) or dropout date (for subjects whose last recorded observation is before dropout) or after the last recorded observation (for subjects whose last recorded observation is on or after dropout), so there is no missing data in these cases. Any observations missing intermittently (not due to the subject dropping out) will be considered missing completely at random (MCAR) and will remain missing with this approach.

For analyses using the FAS-RE analysis sets and for binary endpoints analyzed at each scheduled visit separately, where subjects may dropout for any reason, missing responses for such subjects will also be defined as “non-responsive” at all subsequent visits after the last recorded observation. Any observations missing intermittently (before the last recorded observation) will be considered missing completely at random (MCAR) and will remain missing with this approach.

For analyses using the FAS-OL analysis sets and for binary endpoints analyzed at each scheduled visit separately, where subjects may dropout for any reason except for being a protocol-defined non-responder at Week 12, missing responses for such subjects will also be defined as “non-responsive” at all subsequent visits after the last recorded observation. Any observations missing intermittently (before the last recorded observation) will be considered missing completely at random (MCAR) and will remain missing with this approach.

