### **5.9.2. Prohibited Medications and Treatments**

Subjects are required to discontinue and avoid using certain medications and treatments (see [Section 4.2, Inclusion Criteria](#) and [Exclusion Criteria](#), and [Appendix 3](#)). Subjects should be instructed at each visit to contact the study site investigator promptly if there are any intended changes or additions to concomitant medications.

All medications and treatments that could affect atopic dermatitis must be discontinued except oral antihistamines. Due to the potential to affect atopic dermatitis with ultraviolet light exposure, subjects must also avoid prolonged exposure to the sun and not to use tanning booths, sun lamps or other ultraviolet light sources during the study.

Subjects who received prior treatment with JAK inhibitors are to be excluded from the study.

Herbal medications with unknown properties or known beneficial effects for AD must be discontinued at least 4 weeks before the first dose of investigational product.

Restrictions on certain vaccinations are described in [Section 4.4.2](#).

The Pfizer study team is to be notified of any prohibited medications taken during the study. After consulting with the Medical Monitor, the investigator will make a judgement on the ongoing eligibility of any subject with prohibited medication use during the study.

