### 9.1. Sample Size Determination

A total of 600 subjects with 200 receiving PF-04965842 200 mg QD, 200 receiving PF-04965842 100 mg QD, and 200 receiving placebo (1:1:1 randomization) will provide 94% power to detect a ratio of median time to flare of at least 1.5 times between either dose of PF-04965842 (200 mg or 100 mg) and placebo. The Type I error rate is set at 5% (2-sided). Assuming based on prior data, that about 44% of subjects would meet the protocol-defined criteria to be a responder at Week 12, approximately 1370 subjects would need to enter the open label run-in period of the study to ensure that 600 subjects are available for randomization.

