### **9.2.4. Analysis of Secondary Endpoints**

In general, binary endpoints (such as EASI-50, EASI-90 or the proportion of subjects achieving  $\geq 4$  point improvement in severity of pruritus NRS measure) will be analyzed using the (Cochran-Mantel-Haenszel) test adjusted by randomization strata (age groups) and baseline disease severity. The difference between treatment groups in the proportion of subjects achieving a response along with its 95% confidence interval (using the normal approximation for the difference in binomial proportions) will be reported. If a subject withdraws from the study, then this subject will be counted as a non-responder for endpoints

after withdrawal. In addition, a subject in the FAS-RA subset who receives rescue treatment due to protocol-defined flare will be considered a non-responder.

For continuous endpoints, such as percent change from baseline in the EASI total score and BSA or change from baseline in SCORAD, PSAAD, DLQI/CDLQI, POEM, HADS, and change from baseline in the pruritus severity using the NRS measure, a mixed-effect model with repeated measures (MMRM) will be used. This model will include the factors (fixed effects) for treatment group, randomization strata (age groups), and baseline disease severity, visit, treatment-by-visit interaction, and relevant baseline value. Within the framework of MMRM, differences between groups will be tested using estimates from the MMRM model.

For all binary endpoints, missing data will be handled by considering subjects who withdraw or randomized subjects receiving rescue treatment as non-responders. No imputations will be made for continuous data and missing data will be considered to be MAR.

In general all secondary endpoints will be analysed for the FAS-RA subset. For the subjects requiring rescue therapy (FAS-RE subset), the response achieved at the end of the rescue period will be assessed in relation to the start of the rescue period. In addition to these two analysis sets, secondary endpoints will also be summarized for all subjects participating in the open-label run-in period (FAS-OL subset).

Hypotheses for all relevant secondary endpoints will be tested at the nominal 5% level of significance, without adjustments for multiple comparisons.

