2.2. Study Design

This is a randomized, responder-enriched, double-blind, placebo-controlled, Phase 3 withdrawal trial to evaluate the efficacy and safety of PF-04965842 monotherapy in subjects aged 12 years and older with chronic moderate to severe AD as defined per the inclusion criteria and a body weight ≥ 40 kg.

The trial consists of an open-label run-in period to determine responder status to an initial induction treatment with 200 mg PF-04965842 QD, a randomized, placebo-controlled, double-blinded PF-04965842 maintenance treatment period, and a 4-week untreated follow-up safety period. A study design schematic is presented in [Figure 1](#).

Figure 1. Study Design Schematic

Note: Flare is defined as a loss of response associated with a decrease of at least 50% of the EASI response compared to randomization and an IGA score of ≥ 2 .

Responder criteria are defined as a) achieving an IGA of clear (0) or almost clear (1) (on a 5-point scale), b) a reduction from IGA baseline of ≥ 2 points, and c) reaching an EASI-75 response (at least 75% improvement). Subjects not meeting criteria are declared as non-responders and are not eligible for randomization in this study. They may choose to enroll into the PF-04965842 Long Term Extension (LTE) study B7451015 providing they remain eligible; otherwise, they are permanently discontinued from treatment and enter the 4-week untreated follow-up period in this study.

Responders at the end of the 12-week open-label run-in period enter the 40 week, double-blind, maintenance treatment period in which they are randomized 1:1:1 into either PF-04965842 200 mg QD, PF-04965842 100 mg QD or placebo. Randomization is stratified by age category, ie, <18 years and ≥ 18 years.

Following completion of the 40-weeks of blinded treatment, all subjects are to be assessed for eligibility to enter study B7451015. If a subject discontinues prematurely or is not eligible/willing to participate in B7451015, then the subject enters the 4-week untreated follow-up period.

During the blinded treatment period, subjects meeting the protocol definition of flare enter an open-label rescue period during which they receive another 12-week course of PF-04965842 200 mg QD with topical therapy per local standard of care (SOC). In this study, flare

requiring rescue treatment will be defined as a loss of at least 50% of the EASI response at Week 12 and an IGA score of 2 or higher.

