After completing the 12-week rescue period, eligible subjects may enter study B7451015. Subjects discontinuing early from treatment, or who are otherwise ineligible for the LTE study will undergo a 4 week follow-up period in B7451014.

The total study duration if a subject does not flare is 52 weeks (12 weeks open-label treatment + 40 weeks blinded treatment). The maximum study duration is up to 64 weeks. This would only be achieved if a subject flared on the last day of the maintenance treatment period (52 weeks +12 weeks rescue). If subjects do not intend to enroll in the LTE study, the above durations are extended by +4 weeks of an untreated follow-up period.

A full schedule of activities for the study is provided in [Appendix 7](#).

Sample Size Determination

A total of 600 subjects with 200 receiving PF-04965842 200 mg QD, 200 receiving PF-04965842 100 mg QD, and 200 receiving placebo (1:1:1 randomization) will provide 94% power to detect a ratio of median time to flare of at least 1.5 times between either dose of PF-04965842 (200 mg or 100 mg) and placebo. The Type I error rate is set at 5% (2-sided). Assuming that about 44% of subjects would meet the protocol-defined criteria to be a responder at Week 12, (based on prior data), approximately 1370 subjects would need to enter the open label run-in period of the study to ensure that 600 subjects are available for randomization.

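### For the secondary responder endpoints in the randomized full analysis set, a response held by prohibited AD therapy while the subject stays on blinded drug counts as a response to the randomized arm

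*SAP*

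**What the plan says.** SAP 2.2 describes a trial to "evaluate the efficacy and safety of PF-04965842 monotherapy". Protocol Section 3 bars medicated topical and systemic AD treatment during the run-in and blinded periods, and protocol 5.9 allows medicated topicals only in rescue. Use does not end participation automatically. Under protocol 5.9.2 the sponsor is notified, the Medical Monitor is consulted, and "the investigator will make a judgement on the ongoing eligibility of any subject with prohibited medication use during the study".

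For binary endpoints in FAS-RA, SAP 5.3.1 names one intercurrent event besides dropout: "This intercurrent event (receiving rescue treatment after randomization) may be considered a dropout from randomized treatment". Non-response is assigned from rescue or dropout onward. Protocol 9.2.4 has the same two triggers: withdrawal, and "a subject in the FAS-RA subset who receives rescue treatment due to protocol-defined flare will be considered a non-responder". SAP 5.3.2 treats continuous values as missing after the same two events. None of these sections mentions prohibited AD therapy taken by someone who remains on blinded drug.

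The primary and key secondary endpoints follow other rules. The event is a protocol-defined flare (SAP 6.1.1.1) or a first IGA of 2 or more (SAP 6.2.1.1). Subjects who discontinue without an event are censored at last dose (SAP 5.3.3). Both endpoints are re-analysed in the PPAS (SAP 6.1.1.2 and 6.2.1.2). Protocol 9.2.1 removes from that set anyone who took a prohibited concomitant medication. SAP 4.2 removes users of barred AD therapy, but its explanatory parenthesis lists only high-potency products, systemic drugs and light treatment.

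**The concern.** An IGA of 0 or 1, an EASI-75 or an NRS4 response that is held by a systemic corticosteroid or a medicated topical says little about what the randomized drug maintains alone. Scored as observed, it is credited to the arm.

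Such use is foreseeable. Flare requires both loss of half the EASI response and IGA of 2 or more, and under protocol 5.2 a subject who worsens without meeting both stays on blinded treatment with no medicated topical permitted. After Week 16 the scheduled visits are 12 weeks apart. The SAP itself expects some use: section 4.2 has an exclusion for it, and section 6.6.4 displays concomitant drug treatment for the primary diagnosis.

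At stake are the treatment differences on the secondary responder endpoints, which are tested at a nominal 5% outside the hierarchy, and how far they can be read as monotherapy results.

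**Working it through.** **1. The plan's own figure.** SAP 2.2 says that 200 per arm at two-sided 5% "will provide 94% power to detect a ratio of median time to flare of at least 1.5 times". Under exponential times the hazard ratio is 1/1.5 = 0.667, and the events needed per pairwise comparison (Schoenfeld) are 4 x (1.960 + 1.555)^2 / (ln 1.5)^2 = 4 x 12.36 / 0.1644, about 301 of 400 subjects (75%). Neither document states an event count or a median. Over 40 blinded weeks, 94% is matched by a placebo median of about 16.1 weeks with no dropout, or 11.9 weeks with 30% dropout. Nothing shows the 94% to be wrong, and the point does not depend on it.

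**2. One subject followed through the rules.** A subject starts a barred topical in the blinded period, is allowed to continue, is never rescued and does not drop out.
- Binary endpoints (SAP 5.3.1, protocol 9.2.4): neither trigger applies, so observed values are used and IGA 0/1 or EASI-75 is a response.
- Continuous endpoints (SAP 5.3.2): values are retained.
- Primary and key secondary (SAP 6.1.1.1, 6.2.1.1): no event while EASI and IGA stay below the limits; the subject remains at risk.
- Tipping-point analysis (SAP 5.3.3): not reached, because it imputes only for subjects who discontinue.
- PPAS: excluded under protocol 9.2.1. Under SAP 4.2, exclusion of a lower-potency or non-steroid topical would rest on the general item for other major violations. The responder endpoints are not planned in the PPAS at all (SAP 6.3.1, 6.4.2).

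**3. Size for a responder endpoint.** Let u be the proportion using barred AD therapy while on blinded drug, and s the share of them scored as responders who otherwise would not be. The active-minus-placebo difference shrinks by s x (u placebo - u active). All values are assumed, with s = 0.6:
- 3% placebo, 1% active: 0.6 x 2 = 1.2 points
- 5% placebo, 2% active: 0.6 x 3 = 1.8 points
- 10% placebo, 3% active: 0.6 x 7 = 4.2 points
- 2% placebo, 5% active: 0.6 x (-3) = -1.8 points, so the difference is inflated

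The documents give no expected response rates after randomization, so these shifts cannot be expressed as a share of a planned responder effect.

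**4. Scale for time to event.** With the 16.1-week median, Week 52 flare-free probability is 2^(-40/16.13) = 17.9% on placebo and 2^(-40/24.19) = 31.8% on active, a difference of 13.9 points. The same formula applied here would take 1.2/13.9 = 9%, 1.8/13.9 = 13% or 4.2/13.9 = 30% of it.

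A simulation (4,000 trials per setting, 200 per arm, unstratified log-rank, assumed placebo median 16.8 weeks, true hazard ratio 0.667, no dropout) hid a fraction of would-be flares and censored those subjects at 40 weeks:

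| Hidden, placebo / active | Hazard ratio | Power |
|---|---|---|
| 0% / 0% | 0.66 | 93% |
| 5% / 5% | 0.68 | 88% |
| 10% / 5% | 0.76 | 63% |
| 10% / 0% | 0.82 | 38% |
| 0% / 10% | 0.56 | 99.8% |

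With no true effect (assumed median 20 weeks in both arms), 0% / 10% gave false wins for active in about 33% of trials, against a nominal 2.5%. These settings assume that the flare stays hidden to the end of the period. They show direction and sensitivity and are not a forecast.

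**The case against.** The strongest reply is that the plan already has an answer for the endpoints that matter most. The PPAS removes users for the primary and key secondary endpoints, barred use must be reported and discussed with the Medical Monitor, worsening subjects are told to contact the site for flare assessment, and a user who is withdrawn is already a non-responder. This stands as far as it goes. It leaves the responder endpoints uncovered, and the PPAS drops users on post-randomization behaviour instead of counting the loss of monotherapy response.

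Three stronger readings are tempting, and the documents do not support them.
- A reader might infer that rescue and dropout are the failures in the primary analysis too. They are not: dropout is censored there, and flare itself is the event.
- A reader might say that the same topical is scored in opposite ways according to whether it was permitted. Rescue is more than a topical: the subject has flared, leaves randomized drug and takes open-label 200 mg as well. The user in question remains on the assigned drug.
- A reader might call the result biased outright. That depends on an estimand the documents do not state for this event. Under a treatment-policy reading, observed values are the right ones. Under the monotherapy reading, heavier placebo use makes the comparison with placebo conservative. Only heavier use on active favours the drug, and nothing in the documents shows it.

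**Conclusion.** The gap is real but limited. In FAS-RA no rule addresses prohibited AD therapy taken on blinded drug, so the secondary responder analyses can credit its effect to the randomized arm and then do not answer the monotherapy question. For the primary and key secondary endpoints the PPAS is a partial answer, weakened by its post-randomization exclusions and by SAP wording narrower than the protocol's.

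The size is unknown. The illustrative 1.2 to 4.2 points rest entirely on assumed usage rates and on the assumed 60%, and the sign depends on which arm uses more. The finding supports a should-fix change to the SAP before unblinding. It does not support a claim that the primary test is invalid.

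**What to change.** 1. SAP 5.3.1, FAS-RA: count a subject as non-responsive at all visits after the first blinded-period use of a prohibited systemic, phototherapy or medicated topical treatment for AD. Identify these uses from AD-indicated concomitant-medication records, in a blinded review completed before unblinding.
2. SAP 6.1.1.2 and 6.2.1.2: add a supportive time-to-event analysis that counts that first use as loss of response, unless an event came earlier. Leave the primary analysis unchanged.
3. SAP 4.2: align the PPAS exclusion with protocol 9.2.1.

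For continuous endpoints, setting values to missing after such use should be supportive only. SAP 5.3.2 justifies missing at random after rescue because flare is determined by observed EASI and IGA; starting barred therapy is not determined in that way.

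The cost is SAP text and one derived flag. Protocol 5.9 already has indication (if AD) and start and stop dates recorded, and SAP Section 2 lets the SAP modify the protocol's plans, asking for an amendment only for major changes to the primary endpoint or its analysis. The downside is that a brief use unrelated to worsening would count as failure at every later visit; the blinded review identifies such cases but does not exempt them.

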5.3.2. Continuous Endpoints

For longitudinal continuous endpoints based on the FAS-OL or FAS-RE analysis sets, assuming that the missing data mechanism is missing at random (MAR), the data will be analyzed based on the full likelihood using a linear mixed-effect model with repeated measures for these continuous variables (see [Section 5.2.2](#)). This model will yield unbiased estimates and valid inferences in the presence of a missing data mechanism that is MAR.

In the context of analyses based on the FAS-RA analysis set, subjects requiring to enter the rescue phase of the study are considered dropouts from randomized treatment along with discontinuation from study during double blind period due to any reason. This implies that outcome values after this intercurrent event will be considered missing data. The determination of a protocol-defined flare event (or dropout) is based on past and current values for the total EASI score and the IGA score prior to dropout and not influenced by future (unobserved) values of these assessments beyond dropout. So the mechanism for such a dropout, conditional on the past and current values for total EASI score and IGA score, may be considered MAR. Therefore, the data may be analyzed based on the full likelihood using a linear mixed-effect model with repeated measures for these continuous variables (see [Section 5.2.2](#)). This model will yield unbiased estimates and valid inferences in the presence of a missing data mechanism that is MAR.

In general, for non-PRO continuous endpoints measured longitudinally, missing values post-baseline will not be imputed explicitly. For the continuous PRO variables such as pruritus NRS, DLQI/CDLQI, POEM, PSAAD and HADS, rules (if any) suggested by the developers of these instruments will be followed in calculating the outcome value in the presence of missing data. If these rules are not enough for imputing a value, then the missing values will be handled in the same way as other non-PRO variables.

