5.2.1. Analyses for Binary Data

For analyses where treatment comparisons are relevant, binary data at each scheduled visit will be analyzed by two approaches: (1) the test of hypothesis (and the p-value) between two pairwise treatment groups will be conducted by the Cochran-Mantel-Haenszel (CMH) statistic adjusting for the effect of randomization strata and disease severity (moderate [IGA=3] or severe [IGA=4]) at Study Baseline; p-values will be calculated from the CMH statistic; and (2) the proportion of responders in each treatment group will be summarized along with pairwise differences and their 95% confidence intervals obtained by normal approximation. The difference in proportions will be calculated within each stratum. The final estimate of the difference in proportions will be a weighted average of these stratum-specific estimates using CMH weights. The CMH weight w_k for stratum k ($k = 1, 2, \dots, K$) is given by,

$$w_k = \frac{\frac{n_{ik} n_{ck}}{n_{ik} + n_{ck}}}{\sum_{j=1}^K \frac{n_{ij} n_{cj}}{n_{ij} + n_{cj}}}$$

where n refers to sample size, the subscript c refers to a comparator group and the subscript i refers to a test group. The difference is estimated as $\hat{d} = \sum_{k=1}^K w_k (\hat{p}_{ik} - \hat{p}_{ck})$, where \hat{p} refers to the estimated relative frequency (or proportion of responders).

Two-sided 95% confidence intervals for the difference (based on a normal approximation) are formed by:

$$\hat{d} \pm 1.96 \sqrt{\sum_{k=1}^K w_k^2 \left(\frac{\hat{p}_{ik}(1 - \hat{p}_{ik})}{n_{ik}} + \frac{\hat{p}_{ck}(1 - \hat{p}_{ck})}{n_{ck}} \right)}$$

In the above formula for the variance of \hat{d} (under the square-root sign), when the number of responders is zero ($x = 0$), then \hat{p} will be replaced by $0.5/(n + 1)$. This change will be made only for calculating the variance of \hat{d} and not anywhere else. Estimates of the

difference in proportions along with the two-sided 95% confidence interval will also be provided for the PF-04965842 200 mg QD group versus the PF-04965842 100 mg QD group. No hypotheses will be tested. In analyses of responders, 95% confidence intervals will be calculated for the estimated proportion of response. The confidence interval is based on the normal approximation (or the Clopper-Pearson exact method when there are no or 100% responders).

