5.2.2. Analyses for Longitudinal Continuous Data

Mixed-effect, repeated measures (MMRM) models will be used. Fixed effects for visit, treatment group, treatment-by-visit interaction (where treatment comparisons are relevant), disease severity at Study Baseline and randomization stratification factor will be included in the model. Visit will be modeled as a categorical covariate. Unstructured covariance matrix will be assumed for the model errors. Compound symmetry covariance matrix will be used if the model with unstructured covariance doesn't converge.

When modeling the change from baseline values, the variable for visit will start with the first post-baseline visit, and the actual baseline value will be included as a covariate. At each visit, estimates of least square mean (LSM) values and the pairwise LSM differences between the treatment groups will be derived from the model. The corresponding p-values and 95% confidence intervals will also be derived from the model.

For analyses where treatment comparisons are not relevant, the MMRM model will not have treatment as a factor and only estimates of the LSM values along with their 95% confidence intervals by visit will be reported.

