6.3. Secondary Endpoints (Efficacy)

6.3.1. Response Based on (IGA, EASI-50, EASI-75, EASI-90, EASI-100, NRS4 for Severity of Pruritus, SCORAD50 and SCORAD75, IGA + EASI-75)

	All Randomized Subjects	Randomized Subjects Requiring Rescue Treatment	Pre- Randomization Subjects
Summary	Proportion of subjects achieving a response at Weeks 12, 16, 28, 40 and 52	Proportion of subjects achieving a response at Rescue Weeks 2, 4, 8 and 12	Proportion of subjects achieving a response at Weeks 2, 4, 8 and 12
Population	FAS-RA	FAS-RE	FAS-OL
Baseline	Study (see Section 3.4)	Rescue (see Section 3.4)	Study (see Section 3.4)
Statistical Method	CMH and normal approximation as in Section 5.2.1 .	Normal approximation as in Section 5.2.1 .	Normal approximation as in Section 5.2.1 .
Missing Data	Missing values after dropout are defined as “non-response” (see Section 5.3.1)	Missing values after dropout are defined as “non-response” (see Section 5.3.1)	Missing values after dropout are defined as “non-response” (see Section 5.3.1)

6.3.2. Change from Baseline in (Total EASI Score, SCORAD (VAS) Pruritus and Sleep Sub-Scales, PP-NRS for Severity and Percent BSA)

	All Randomized Subjects	Randomized Subjects Requiring Rescue Treatment
Summary	Change from baseline at Weeks 12, 16, 28, 40 and 52	Percent change/Change from baseline at Rescue Weeks 2, 4, 8 and 12
Population	FAS-RA	FAS-RE
Baseline	Study (for Week 12); Randomization (for visits after Week 12) (see Section 3.4)	Rescue (see Section 3.4)
Statistical Method	MMRM as in Section 5.2.2	MMRM as in Section 5.2.2
Missing Data	Use observed data (see Section 5.3.2)	

Change from Study Baseline at Week 12 and its 95% CI will be estimated for each randomized treatment group using an MMRM analysis using data from Weeks 2, 4, 8 and 12. For PP-NRS, data will be included from Days 2 – 15, Weeks 4, 8 and 12.

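### The SAP's MAR argument for rescue dropout rests on EASI and IGA, but the PRO and itch MMRMs contain no post-baseline EASI or IGA, so the argument does not carry over to them

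*SAP*

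**What the plan says.** SAP 5.3.2 counts entry to rescue as dropout from randomized treatment, together with "discontinuation from study during double blind period due to any reason", and sets later values to missing. Its case for MAR is that flare is decided by scores already seen. The mechanism, "conditional on the past and current values for total EASI score and IGA score, may be considered MAR", is then taken to permit the likelihood-based MMRM. The section closes: "This model will yield unbiased estimates and valid inferences in the presence of a missing data mechanism that is MAR". PROs fall back to the same handling once the instrument developers' rules are exhausted.

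SAP 5.2.2 gives the model terms: "Fixed effects for visit, treatment group, treatment-by-visit interaction (where treatment comparisons are relevant), disease severity at Study Baseline and randomization stratification factor". In addition, "the actual baseline value will be included as a covariate". Section 5.2.1 defines the severity factor as "disease severity (moderate [IGA=3] or severe [IGA=4]) at Study Baseline". For the FAS-RA change-from-baseline analyses (6.3.2 and 6.4.1), the baseline is "Study (for Week 12); Randomization (for visits after Week 12".

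SAP 3.1 defines flare by an EASI threshold built from Study Baseline and Week 12 EASI, together with an IGA of 2 or more.

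**The concern.** MAR is always relative to a conditioning set. Dropout that is MAR given EASI and IGA need not be MAR given only the past DLQI, POEM or itch scores. A flared subject's missing DLQI values are predicted from subjects with a similar DLQI history who did not flare, and who therefore tended to have milder skin disease. If skin severity also carries information about later DLQI, those predictions are too favourable. This matters most in the arm with most rescue, presumably placebo, and so shrinks the drug-placebo difference.

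These are listed secondary endpoints. They are reported with p-values and confidence intervals and tested at a nominal 5% level (SAP 5.1). The only sensitivity analysis planned for missing data is the tipping point for event times (5.3.3, Appendix 6). None is planned for continuous endpoints.

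**Working it through.** The plan states no figure on this point, so there is none to reproduce. The check has two parts.

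**1. Conditioning sets side by side**

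| Quantity that decides flare (SAP 3.1) | In the PRO and itch MMRMs (5.2.2)? |
|---|---|
| Study Baseline EASI | No |
| Week 12 EASI | No |
| Post-randomization EASI | No |
| Post-randomization IGA | No |
| Study Baseline IGA (3 or 4) | Yes, as severity; not part of the flare rule |

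Two endpoints differ. Percent BSA is summed from the EASI handprint counts (Protocol 7.7.3.1), so its own history carries part of EASI and the gap is smaller. The EASI model has its own history but no post-baseline IGA. After Week 12 its baseline covariate is the Randomization Baseline, so Study Baseline EASI, which helps set the flare threshold, is absent.

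**2. Simulation of the consequence**

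All inputs here are assumptions. There were 400,000 subjects over two arms and four post-randomization visits. EASI and IGA were noisy readings of one latent severity, and the PRO shared that latent with loading ρ. Data were dropped after any visit meeting an EASI-and-IGA flare rule. The target was the Week 52 difference had no one been rescued, which matches the SAP's treatment of post-rescue values as missing. Fitting used sequential regression with arm-specific intercepts and common slopes, the likelihood fit for monotone dropout. Age and severity strata were left out.

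Bias (%) = 100 × (estimated difference ÷ true difference − 1). Example, ρ = 0.7 with about 53% of placebo missing: 100 × (−1.018 ÷ −1.099 − 1) = −7.4%.

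| PRO-EASI correlation | Missing at Week 52, placebo/active | Own history (as in SAP) | + EASI | + EASI and IGA |
|---|---|---|---|---|
| 0.00 | 53/19% | −0.2% | −0.2% | −0.2% |
| 0.25 | 53/19% | −3.1% | −0.4% | −0.1% |
| 0.43 | 53/19% | −5.1% | −0.6% | 0.0% |
| 0.61 | 53/19% | −7.4% | −0.5% | +0.4% |
| 0.80 | 53/19% | −10.6% | −1.1% | +0.3% |
| 0.00 | 66/30% | −0.4% | −0.5% | −0.5% |
| 0.25 | 66/30% | −4.0% | −1.2% | −0.3% |
| 0.43 | 66/30% | −6.6% | −1.6% | −0.1% |
| 0.61 | 66/30% | −9.8% | −2.5% | 0.0% |
| 0.80 | 66/30% | −14.3% | −3.8% | +0.1% |

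(Missing percentages are approximate.) In the zero-correlation rows, dropout is unrelated to the PRO by construction, so departures of a few tenths of a percent are simulation noise. At ρ = 0.7 and the lower missingness, the placebo mean was 1.469 against a true 1.601 (short by 0.132) and the active mean 0.451 against 0.503 (short by 0.051). Both arms are predicted too favourably, placebo more so. The EASI model itself was biased by −2.7 to −3.4% at the lower missingness and −7.6 to −8.3% at the higher, because IGA also drives flare.

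**Other assumed inputs**

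- Placebo flare 66 to 80%, correlation 0.25 to 0.59: understated by 4 to 17%; within 2% with EASI and IGA added.
- Placebo flare 58 to 71%, correlation 0.3 to 0.7, stable disease after withdrawal: true −2.4, MMRM −1.2 to −1.5, so understated by 38 to 50%. Progressive worsening: true −2.7, MMRM −1.5 to −1.8, so 33 to 44%. With EASI alone added, the progressive case gave −3.4, an overstatement of 3.4 ÷ 2.7 − 1 = 26%.
- Placebo flare 61 to 73%, correlation about 0.2 to 0.65: 43 to 48% (stable) and 22 to 24% (progressive). These rise to 56 to 60% and 35 to 36% if half of the flare-visit PRO values are lost. With EASI and IGA added, including the flare visit, the error fell to 15 to 17% and 7 to 8%.

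Loss of flare-visit values can occur under the visit windows. SAP Appendix 2 keeps the visit nearest the target day. A flare found at an unscheduled visit on Day 140, after a Day 113 visit, falls in the Week 16 window (Days 100 to 155). It is 27 days from target against 0, so it is not used.

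**The case against.** A reader might infer three stronger things, and the documents support none of them.

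- **That these models contain neither score.** Every MMRM carries the Study Baseline IGA category, and BSA is built from EASI components. What is absent is post-baseline EASI and IGA.
- **That the unbiasedness statement is false.** It is conditional on MAR and correct as worded. The unsupported part is the premise, for these endpoints.
- **That the SAP's own reasoning proves bias.** Losing a reason for MAR leaves the assumption unsupported; it does not show that it is violated. If a PRO is unrelated to EASI, the bias is essentially nil, and the documents give no correlation for any of these instruments.

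Other objections carry weight. The simulated sizes differ several-fold, and no input comes from the documents. The error generally runs against the drug, so it is conservative for a claim over placebo, whereas adding EASI alone overshot in one scenario. The endpoints lie outside the test hierarchy. The responder analyses for NRS4, SCORAD-50/75 and PtGA count rescued subjects as non-responders and do not use this assumption. That last point does not help DLQI/CDLQI, POEM, HADS or PSAAD, whose analyses in 6.4.1 are by MMRM only.

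**Conclusion.** The concern holds as a gap in justification with a probable, unquantified bias. The SAP supports MAR by conditioning on EASI and IGA, then uses models for the PRO, itch and SCORAD-subscale endpoints that leave out the post-baseline values. BSA is affected less, and the EASI model has a smaller version of the same gap. The argument also says nothing about discontinuation for reasons other than flare.

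Where EASI and IGA predict the later outcome beyond its own history, the drug-placebo difference after Week 16 is likely to be biased, generally toward no difference. The size is a range set by assumption: about nil with no PRO-EASI relation, 3 to 17% in two simulations, and 22 to 60% in two others with different assumed trajectories. No single figure should be quoted. The 200 mg versus 100 mg comparison was not simulated. The primary and key secondary time-to-event tests are unaffected. This is a cheap improvement to secondary analyses.

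**What to change.** 1. In SAP 5.3.2, limit the MAR statement to what each model conditions on. Say that the EASI/IGA argument does not by itself cover the PRO, itch and SCORAD-subscale models, or discontinuation for other reasons.
2. For these endpoints in FAS-RA, add multiple imputation under MAR, with post-baseline EASI and IGA jointly as auxiliary variables. Include the flare visit even where Appendix 2 would drop it. Include Study Baseline and Week 12 EASI, since they set the flare threshold. Analyse each imputed set with the 5.2.2 model, pool the results, and report them alongside the plain MMRM.
3. Use EASI and IGA together; EASI alone left more bias or overshot.

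The scores are already collected at every site visit, so the cost is programming and a specified imputation model. The downside is residual model dependence. If disease worsens progressively and the imputation model is misspecified, the estimate could overshoot in the drug's favour, which is a reason to show both analyses. The method stays within MAR, so it does not replace a non-MAR sensitivity analysis for continuous endpoints.
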